6.6 Additional treatment guidance

6.6.1 Treatment compliance

The investigator must promote compliance by instructing the participant to take the study treatment exactly as prescribed and by stating that compliance is necessary for the participant's safety and the validity of the study. The participant must also be instructed to contact the investigator if he/she is unable for any reason to take the study treatment as prescribed, and to complete the participant diary. Compliance will be assessed by the investigator and/or study personnel at each visit using pill counts and information provided by the participant. This information should be captured in the source document at each visit.

Emergency code breaks must only be undertaken when it is required to in order to treat the participant safely. Blinding codes may also be broken after a participant discontinues treatment due to disease progression if deemed essential to allow the investigator to select the participant' s next treatment regimen, and after discussion and agreement with Novartis. Most often, study treatment discontinuation and knowledge of the possible treatment assignments are sufficient to treat a study participant who presents with an emergency condition. Emergency treatment code breaks are performed using the IRT. When the investigator contacts the system to break a treatment code for a participant, he/she must provide the requested participant identifying information and confirm the necessity to break the treatment code for the participant. The investigator will then receive details of the investigational drug treatment for the specified

participant and a fax or email confirming this information. The system will automatically inform the Novartis monitor for the site and the study team that the code has been broken.

It is the investigator's responsibility to ensure that there is a dependable procedure in place to allow access to the IRT/code break cards at any time in case of emergency. The investigator will provide:

- protocol number
- study drug name
- participant number

In addition, oral and written information to the participant must be provided on how to contact his/her backup in cases of emergency, or when he/she is unavailable, to ensure that un-blinding can be performed at any time.

After the emergency break the participant must be discontinued from the study by the investigator.

6.7 **Preparation and dispensation**

Each study site will be supplied with study drug in packaging as described under investigational and control drugs Section 6.1.1.

The study drug packaging has a 2-part label. A unique medication number is printed on each part of this label which corresponds to a certain treatment. Investigator staff will identify the study drug package(s) to dispense to the participant by contacting the IRT and obtaining the medication number(s). Immediately before dispensing the package to the participant, investigator staff will detach the outer part of the label from the packaging and affix it to the source document (Drug Label Form) for that participant's unique participant number.

As per Section 4.6, during a public health emergency as declared by Local or Regional authorities, i.e; pandemic, epidemic or natural disaster, that limits or prevents on-site study visits, delivery of IMP directly to a participant's home may be permitted (if allowed by Local or Regional Health Authorities and Ethics Committees as appropriate) in the event the Investigator has decided that an on-site visit by the participant is no longer appropriate or possible, and that it is in the interest of the participant's health to administer the study treatment even without performing an on-site visit. The dispatch of IMP from the site to the participant's home remains under the accountability of the Investigator. Each shipment/provisioning will be for a maximum of 8-weeks supply. In this case, regular phone calls or virtual contacts (aligned with the protocol visit schedule in Table 8-1) will occur between the site and the participant for instructional purposes, safety monitoring, investigation of any adverse events, ensuring participants continue to benefit from treatment, and discussion of the participant's health status until the participants can resume visits at the study site. Where assessment of suitability for continued IMP administration is required (e.g. a protocol required negative urine pregnancy test in WOCBP) the participant will be instructed by site on their requirements to perform these procedures remotely and the communication process with site prior to participant selfadministration.

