Discontinuation from study	Point/time when the participant permanently stops receiving the study treatment and further protocol required assessments or follow-up, for any reason. No specific request is made to stop the use of their samples or data.		
Discontinuation from study treatment	Point/time when the participant permanently stops receiving the study treatment for any reason (prior to the planned completion of study drug administration, if any). Participant agrees to the other protocol required assessments including follow-up. No specific request is made to stop the use of their samples or data.		
Dosage	Dose of the study treatment given to the participant in a time unit (e.g. 100 mg once a day, 75 mg twice a day)		
Electronic Data Capture (EDC)	Electronic data capture (EDC) is the electronic acquisition of clinical study data using data collection systems, such as Web-based applications, interactive voice response systems and clinical laboratory interfaces. EDC includes the use of Electronic Case Report Forms (eCRFs) which are used to capture data transcribed from paper source forms used at the point of care		
End of the clinical trial	The end of the clinical trial is defined as the last visit of the last participant or at a later point in time as defined by the protocol		
Enrollment	Point/time of participant entry into the study; the point at which informed consent must be obtained (i.e. prior to starting any of the procedures described in the protocol). The action of enrolling one or more participants.		
Estimand	As defined in the ICH E9(R1) addendum, estimand is a precise description of the treatment effect reflecting the clinical question posed by the trial objective. It summarizes at a population-level what the outcomes would be in the same participants under different treatment conditions being compared. Attributes of an estimand include the population, variable (or endpoint), as well as the specification of how the remaining intercurrent events are addressed and a population-level summary for the variable.		
Healthy volunteer	A person with no known significant health problems who volunteers to be a study participant		
Intercurrent events	Events occurring after treatment initiation that affect either the interpretation or the existence of the measurements associated with the clinical question of interest.		

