6.4 Treatment blinding

This is a double-blind study: participants, investigator staff, persons performing the assessments, and Novartis clinical trial team (or delegates) will remain blinded to the identity of study treatments from the time of randomization (until final database lock), using the following methods:

- 2. Randomization data will be kept strictly confidential until the time of final database lock and will not be accessible by anyone else involved in the study with the exceptions in Table 6-4.
 - a. The randomization codes will be disclosed to an independent analysis team to prepare safety and efficacy reports for the DMC. The independent analysts will keep randomization data confidential until data base lock. Data will be shared with the study team under blinded conditions.
- 3. The identity of the treatments will be concealed by the use of placebo that are each identical in packaging, labeling, schedule of administration, appearance, taste and odor to the respective active treatment. Placebo capsules/tablet will be given in active treatment groups when needed to maintain blinding as described in Section 6.1.3.

A double-dummy design is used because the identity of the study treatment cannot be disguised, as the drug products are visibly different.

Unblinding will only occur in the case of participant emergencies (see Section 6.6.2) and at the conclusion of the study. Unblinding a single participant's treatment at a site for safety reasons (necessary for participant management) will occur via an emergency system in place at the site. As a result the participant should be discontinued from the study treatment.

At the time of safety review, the DMC will review unblinded reports created by an independent analysis team. More details will be provided in the DMC charter.

Table 6-4Blinding and unblinding plan

Time or Event				
Role	Randomizatio n list generated	Treatment allocation & dosing	Safety event (single participant unblinded)	Safety review
Participants	В	В	В	В
Site staff	В	В	UI	В
Novartis CTT	В	В	UI	В
Global Clinical Supply	UG	В	UI	В
Randomization Office	UI	UI	UI	UI
Unblinded Pharmacovigilance sponsor staff	В	UI	UI	В
Statistician/statistical programmer	В	В	UI	В
Data Monitoring Committee(DMC) and independent statistician/programmer supporting DMC	UI	UI	UI	UI
All other sponsor staff not identified above (i.e. trial team, project team, management & decision boards, support functions)	В	В	В	В

Key:

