¹¹ Women Of Child Bearing potential (WOCBP) must have a urine dipstick pregnancy test every 4 weeks, including at week 28, 36 and 44 (when there are no study visits), up to and including the follow up visit.

¹² After Baseline visit onwards serum sample to be collected for serum pregnancy test only if urine dipstick test is positive – During the study if test is positive, the participant must be discontinued from study drug.

¹⁷ At Baseline and week 4, to be collected at least 1-2 hours post dose at clinic.

¹⁸ Update as necessary

¹⁹ Update as necessary - SAEs must be reported & recorded until 30 days after the participant has stopped study participation; see appropriate protocol Section 10.1.2.

²¹ For participants who discontinue study treatment prematurely before the end of the treatment period for any reason other than withdrawal of informed consent, the Week 48, End of Treatment (EOT) and Week 52 End of Study (EOS) visits must be performed.

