9.1 Discontinuation from study treatment and from study

9.1.1 Discontinuation from study treatment

Discontinuation of study treatment for a participant occurs when study treatment is permanently stopped for any reason (prior to the planned completion of study drug administration) and can be decided by either the participant or the investigator.

The investigator must discontinue study treatment for a given participant if, he/she believes that continuation would negatively impact the participant's well-being.

Discontinuation from study treatment is required under the following circumstances:

- participant/guardian decision
- Pregnancy (see Section 8.4.3 and Section 10.1.4)
- Any situation in which continued study participation might result in a safety risk to the participant (including life-threatening events considered to be related to study medication)
- Following emergency unblinding
- Emergence of the following adverse events:

- For ALT, AST, TBL and/or alkaline phosphatase elevations mandating study treatment discontinuations (see Sections 10.2.1 and Section 16.2 for further instructions and monitoring).
- Any evidence of liver decompensation as defined by ascites, bleeding esophageal varices, hepatic encephalopathy, jaundice.
- Serious COVID-19 infection requiring hospitalization

If the decision of discontinuing the study medication comes from the participant, the investigator should make a reasonable effort to understand the primary reason for the participant's discontinuation from study treatment and record this information.

Participants who discontinue from study treatment agree to return for the end of treatment and follow up visits indicated in the assessment schedule (Table 8-1).

If the participant cannot or is unwilling to attend any visit(s), the site staff should maintain regular telephone contact with the participant, or with a person pre-designated by the participant. This telephone contact should preferably be done according to the study visit schedule.

After discontinuation from study treatment, at a minimum, the following data should be collected at clinic abbreviated visits or via telephone/email contact:

- New / concomitant treatments
- Adverse Events / Serious Adverse Events

The investigator must also contact the IRT to register the participant's discontinuation from study treatment.

If discontinuation occurs because treatment code has been broken, please refer to Emergency breaking of treatment code see Section 6.6.2.

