9.1.2 Discontinuation from study

Discontinuation from study is when the participant permanently stops receiving the study treatment, and further protocol-required assessments or follow-up, for any reason.

If the participant agrees, a final evaluation at the time of the participant's study discontinuation should be made as detailed in the assessment table (refer to Section 8).

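### Section 6.6.2 takes a participant out of the study after an emergency code break, while 9.1.1 and Table 8-1 footnote 21 keep that participant's later visits

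*Protocol*

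**What the plan says.** Protocol 6.6.2, on emergency breaking of the treatment code, closes with: "After the emergency break the participant must be discontinued from the study by the investigator".

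Protocol 6.4, on unblinding one participant at a site for safety, says: "As a result the participant should be discontinued from the study treatment". It does not mention visits.

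Protocol 9.1.1 includes "Following emergency unblinding" in its list of reasons for stopping study treatment. It adds: "Participants who discontinue from study treatment agree to return for the end of treatment and follow up visits indicated in the assessment schedule". It then sends these cases back to 6.6.2: "If discontinuation occurs because treatment code has been broken, please refer to Emergency breaking of treatment code see Section 6.6.2".

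Table 8-1 footnote 21 covers every premature stop of study treatment except withdrawal of consent, and states that "the Week 48, End of Treatment (EOT) and Week 52 End of Study (EOS) visits must be performed".

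The two terms are defined separately. For stopping study treatment, the glossary says: "Participant agrees to the other protocol required assessments including follow-up". For leaving the study, 9.1.2 says: "Discontinuation from study is when the participant permanently stops receiving the study treatment, and further protocol-required assessments or follow-up, for any reason".

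**The concern.** The same event leads to two different states of follow-up, depending on which section the site reads. Because both terms are defined, 6.6.2 cannot be passed off as loose wording: taken literally, it ends the assessments that 9.1.1 and footnote 21 require. The reference in 9.1.1 makes this worse, because it leads a site from the instruction that keeps the visits to the one that drops them.

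What is at stake is the primary endpoint for participants unblinded after Week 24. For early treatment stops after Week 24, the estimand (Protocol 2.1 and 12.4.3, intercurrent event 4) uses a treatment-policy strategy and asks for the Week 48 biopsy. A site that obeys 6.6.2 may never schedule it.

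**Working it through.** The point is one of consistency, so the check sets the current texts side by side.

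| Place | What stops after an emergency break | What happens to later visits |
|---|---|---|
| 6.6.2 | Study participation (mandatory) | Ended, by the 9.1.2 definition |
| 6.4 | Study treatment (recommended) | Not mentioned |
| 9.1.1 | Study treatment (required) | End-of-treatment and follow-up visits kept |
| Table 8-1 footnote 21 | Study treatment, any reason but consent withdrawal | Week 48 and Week 52 visits mandatory |

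**Step 1: which pairs conflict.** By definition, leaving the study includes stopping treatment. Obeying 6.6.2 therefore also satisfies 6.4 and the list item in 9.1.1. It does not satisfy the visit requirements in 9.1.1 and footnote 21. That is the only real clash.

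**Step 2: breaks before Week 24.** Event 4 already makes these participants non-responders, and the biopsy footnote to Table 8-1 makes their Week 48 biopsy optional. The primary outcome does not change.

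**Step 3: breaks after Week 24.** If the site follows 6.6.2, no Week 48 visit is scheduled. Two routes remain.

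- *An early-termination biopsy exists.* Section 12.4.4 would use it after at least 24 weeks of treatment. Section 8 offers people leaving the study a final evaluation if they agree, but the EOS/PSW column of Table 8-1 shows no biopsy. SAP 2.5 plans such a biopsy where possible, but that SAP is dated December 2019 and describes the three-arm, 210-patient design. Section 8.3.1.8, on liver biopsy, is not in the text available to this review.
- *No biopsy exists.* Section 12.4 lists early stopping of treatment before Week 48 as an intercurrent event without limiting the reason. It then counts participants with no Week 48 biopsy as non-responders, as does event 4 in 12.4.3. Section 12.4.4 is headed as dealing with missing values unrelated to intercurrent events. One sentence there would impute endpoints that follow intercurrent events, which fits poorly with its heading. Non-response is the better-supported reading.

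**Step 4: size.** The number of outcomes affected is 380 × (code-break rate) × (share of breaks after Week 24) × (share who would otherwise have had a Week 48 biopsy). Only the 380 is given. Each percentage point of code-break rate is 380 × 0.01 = 3.8 participants over four arms, before the two shares reduce it. Section 12.8.1 anticipates about 20% missing Week 48 biopsies overall, but nothing shows that this applies to people who stopped treatment in an emergency. The calculation ends there.

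**The case against.** The best defence is that 6.6.2 is the specific rule. Both 6.4 and 9.1.1 refer to it, and following it breaks neither of their instructions to stop treatment. The gap in follow-up is also narrower than the definitions suggest. Section 8 still offers a final evaluation to someone leaving the study. In the other direction, 6.1.4 lets a participant continue off treatment only if participant and investigator agree, and otherwise provides a treatment-discontinuation visit. So the treatment-only reading does not guarantee a Week 48 biopsy either.

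Much of this stands. It rules out saying that 6.4 keeps the Week 48 and Week 52 visits, because 6.4 is silent on visits. It also means that the whole difference between having and not having a Week 48 biopsy cannot be charged to 6.6.2.

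It does not remove the conflict. Section 9.1.1 itself classes emergency unblinding as a stop of study treatment before it refers onward, footnote 21 excepts only withdrawal of consent, and 6.1.4 says that stopping treatment is not withdrawal from the study. The protocol gives no reason for ending the assessments of an unblinded participant.

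**Conclusion.** The conflict is real and lies in the current text: 6.6.2 against the visits retained by 9.1.1 and Table 8-1 footnote 21. For breaks after Week 24 it can forfeit a biopsy that the treatment-policy strategy asks for. Without an early-termination biopsy, the participant most plausibly becomes a non-responder. That reading rests on section 12.4, and on a safety-driven code break ordinarily counting as an adverse-event stop under event 4.

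The number affected is unknown and probably small. A reader might infer three stronger things that the documents do not support:

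- *A measurable loss of power.* Any such figure would rest on an assumed code-break rate and assumed timing.
- *An outcome left open between non-response and imputation.* Section 12.4 goes most of the way to settling it.
- *Loss of safety follow-up.* Sections 6.5.4, 9.3, 10.1.1 and 10.2.1 largely keep adverse-event and liver follow-up going after treatment stops.

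The correction is worth making because 6.6.2 is a wrong rule rather than a missing detail, and it is nearly free to put right.

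**What to change.** In the last sentence of 6.6.2, replace *discontinued from the study* with *discontinued from study treatment*. Add one sentence saying that the visits in 9.1.1 and Table 8-1 footnote 21 still apply, including the Week 48 biopsy if treatment stopped after Week 24.

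A separate statement assigning code breaks to intercurrent event 4 is largely redundant, because 12.4 already covers early stopping of treatment for any reason.

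The cost is one sentence changed and one added at the next protocol amendment. It adds no procedure beyond those already planned and does not change the analysis. The edit does not settle when the end-of-treatment visit falls after an early stop (Section 8 asks for it promptly, and 9.3 places follow-up four weeks after the last treatment), but the visits are kept under either timing.

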6.7.1 Handling of study treatment and additional treatment

6.7.1.1 Handling of study treatment

Study treatment must be received by a designated person at the study site, handled and stored safely and properly and kept in a secured location to which only the investigator and designated site personnel have access. Upon receipt, all study treatment must be stored according to the instructions specified on the labels and in the IB.

Clinical supplies are to be dispensed only in accordance with the protocol. Technical complaints are to be reported to the respective Novartis Country Organization (CO) Quality Assurance.

Medication labels will be in the local language and comply with the legal requirements of each country. They will include storage conditions for the study treatment but no information about the participant except for the medication number.

The investigator must maintain an accurate record of the shipment and dispensing of study treatment in a drug accountability log. Monitoring of drug accountability will be performed by monitors during site visits or remotely and at the completion of the trial. Participants will be asked to return all unused study treatment and used/unused packaging at the end of the study or at the time of discontinuation of study treatment.

The site may destroy and document destruction of unused study treatment, drug labels and packaging as appropriate in compliance with site processes, monitoring processes, and per local regulation/guidelines. Otherwise, at the conclusion of the study, and as appropriate during the course of the study, the investigator will return all unused study treatment, packaging, drug labels, and a copy of the completed drug accountability log to the Novartis monitor or to the Novartis address provided in the investigator folder at each site.

6.7.2 Instruction for prescribing and taking study treatment

Participants should be instructed to take the dose of study medication daily, close to the evening meal; either just prior to (within 5 minutes) consuming the evening meal, or no more than 30 minutes after consuming the evening meal and at about the same time each day. Only at Baseline and week 4 visit, the participants should take their doses at the clinic following a meal instead of in the evening.

Once the protocol amendment v02 is approved and after the tropifexor (LJN452) 10, 30 and 100 μ g and matching placebo hard gelatin capsule supply is depleted, the participant will receive 9 blister packs in a box (10 mg licogliflozin or matching placebo tablets) and 1 bottle of 140 μ g hard gelatin capsules (replacing the 10, 30 and 100 μ g tropifexor or matching placebo capsules) for each 4 week period every 4 weeks through Week 20. At the Week 24, Week 32 and Week 40 visits 2 sets of 4 week supplies of study medication will be distributed to accommodate the 8 weekly visit schedule (Table 8-1). The participants will take **3 tablets** from the blister pack and **1 capsule** from the bottle daily as described above.

If the COVID-19 or other pandemic prevents on-site visits the site may arrange delivery of study medication to a participant's home.

Novartis Amended Protocol Version 02 (Clean) Confidential

6.7.2.1 Overview of treatment - type and number of capsules and tablets taken per day

The 140 μ g dose of tropifexor and its matching placebo are each available as a single hard gelatin capsule. Participants on the study at the time of availability of the single tropifexor/placebo capsule, may continue on the 3-capsule tropifexor (100 μ g + 30 μ g + 10 μ g) or matching placebo regimen, as shown in Table 6-5, until the available 3 capsule supply is depleted.

	·····				······································			
Treatme nt Arm	Tropifexor (LJN452) 10µg capsu le	Tropifexor (LJN452) 30µg capsu le	Tropifexor (LJN452) 100µg capsule	Tropifexor (LJN452) Placebo capsule	Licogliflozi n (LIK066) 10mg table t	Licogliflozi n (LIK066) Placebo tablet	Frequency	
Arm A	1	1	1	0	3	0	Daily	
Combo Tropifexor (L JN452) 140 µg								
& Licogliflozin (LIK066)								
30 mg								
Arm B	1	1	1	0	0	3	Daily	
Mono Tropifexor (L JN452) 140 µg								
Arm C	0	0	0	3	3	0	Daily	
Mono Licogliflozin (LIK066) 30 mg								
Arm D	0	0	0	3	0	3	Daily	
Placebo								

Table 6-5Dosing with 3 capsule (10 + 30 + 100 µg) tropifexor supply

After the 3-capsule supply is depleted, participants will take 1-capsule of 140 µg tropifexor or matching placebo daily as described in Table 6-6. No change is made to licogliflozin dosing.

Novartis Amended Protocol Version 02 (Clean) Confidential

Table 6-6	Dosing with single capsule (140 μg) tropifexor supply						
Treatment Arm	Tropifexor (LJN452) 140µg capsule	Tropifexor (LJN452) Placebo capsul e	Licogliflozin (LIK066) 10mg tablet	Licogliflozin (LIK066) Placebo tablet	Frequency		
Arm A Combo Tropifexor (LJN45 2) 140 μg & Licogliflozin (LIK06 6) 30 mg	1	0	3	0	Daily		
Arm B Mono Tropifexor (LJN45 2) 140 μg	1	0	0	3	Daily		
Arm C Mono Licogliflozin (LIK06 6) 30 mg	0	3	3	0	Daily		
Arm D Placebo	0	3	0	3	Daily		

IMPORTANT: Please ensure that the date of the change, and the number of capsules (from 3 capsule to 1 capsule) is accurately captured in the eCRF Change in Dosing log for each participant.

Dosing recommendations:

1. Participants should take 3 Tablets from the blister pack (licogliflozin or matching placebo) & 1 or 3 Capsules (tropifexor or matching placebo) depending on current supply close to the evening meal; either just prior to (within 5 minutes) consuming the evening meal, or no more than 30 minutes after consuming the evening meal, at about the same time each day. Participants directed to take 3 capsules must be reminded that one capsule is to be taken from each of the 3 tropifexor/placebo bottles provided. At Baseline and week 4 the dose will be taken in the morning at the clinic close to a meal instead of in the evening.

Confidential

- 4. Participants should be instructed to swallow the capsules and tablets whole and not to chew them.
- 5. If vomiting or diarrhea occurs during the course of treatment, no re-dosing of the participant is allowed before the next scheduled dose.
- 6. If a dose is missed and not remembered the same day, it should not be made up on a subsequent day.

All kits of study treatment assigned by the IRT will be recorded/databased in the IRT system.

The investigator must promote compliance by instructing the participant to take the study treatment exactly as prescribed and by stating that compliance is necessary for the participant's safety and the validity of the study. It should be emphasized to the participant that the contents of the study medication bottles are not identical; the participant must take one capsule from EACH bottle and 3 tablets from the blister pack each day. The participant must also be instructed to contact the investigator if for any reason he/she has not taken the study treatment as prescribed.

At site dosing – Baseline and Week 4:

- Participants should take study drug either just prior to (within 5 minutes) consuming the morning meal, or no more than 30 minutes after consuming the morning meal.
- Participants should be instructed to swallow whole capsules and not to chew or open them.
- If vomiting occurs during the course of treatment, participants should not take the study treatment again before the next scheduled dose.
- No evening dose should be taken on the days of the Baseline and Week 4 visits as the daily dose is taken at the site on those 2 days.

Novartis	Confidential	Page 90 of 160
Amended Protocol Version 02 (Clean)		Protocol No. CLJN452D12201C

